Research assistants will be asked to document field notes at the time of consent to capture information on the length of time taken for the consent, if the participant had others present, and observations during the process of the consent (e.g. discussion by the participant with an attendant or family member)

If women are unconscious or in a mental state where they are unable to consent for themselves, an attendant or guardian will be approached for consent. As women in this condition are at high risk for morbidity and/or mortality inclusion in this study is key to achieve the objectives of reducing this risk. Additionally, women in this condition are the most likely to gain direct benefit from vital sign monitoring. As such if an attendant is not available the woman will be enrolled without consent to enable monitoring to begin immediately. Consent will be sought as soon as possible after the woman regains capacity to consent or an attendant becomes available. If the woman and/or her attendant declines to participate at that time all study procedures will be discontinued.

Study Procedures

1. A group meeting detailing the study background, procedures, risks and benefits will be held for all clinical providers in the department prior to study initiation.
2. We will obtain informed consent for clinicians and peripartum women admitted for delivery as described above.
3. A 2-hour training session on the use of the wireless monitoring system, nature of alerts and emergency mobile phone will be held for enrolled clinicians at a time convenient to them.
4. Alternative two-week blocks will be assigned to “intervention” vs “control”. During an “intervention block” all women delivering by emergency cesarean and consenting to participate will be monitored using the wireless device for the first 24 hours after delivery. During a “control

block" standard of care for monitoring will be used and women delivering via emergency cesarean will have record review only.

5. Maternity ward coverage schedules for enrolled specialist and midwives will be obtained. This will be used to determine the clinicians on call during each intervention block.
6. During the intervention block, midwives present in the theatre will be asked to perform the following tasks for any emergency cesarean deliveries s/he is present for:
 - a. Placement of the biosensor on any enrolled women s/he delivers by emergency cesarean delivery immediately after completion of the surgery.

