Cardiopulmonary resuscitation	Emergency procedures including chest compressions and lung ventilation.

12. The research assistant will also extract data on (age, district of origin, education level, occupation, referred in from another facility), obstetric history (parity, gestational age at delivery, antenatal complications) and medical comorbidities (HIV, chronic hypertension, cardiac, pulmonary or kidney disease). Information on timing of delivery, indication for cesarean

delivery and decision to incision time for emergency caesarean delivery, documentation of physiologic signs will also be extracted. *See Appendix 1 – Chart Review*

13. At the end of each clinical duty or shift enrolled midwives and specialist doctors will be asked to complete a brief questionnaire which will be administered via electronic survey using redcap survey on the responder phone. This will be to assess if the midwife received any alerts, how they responded and if it influenced clinical management. *See Appendix 2 – Call Duty Follow up Questionnaire. This is estimated to take ~5-10mins to complete.*

14. Up to 30 enrolled clinicians who participated in the monitoring system will also be approached at a convenient time for a in depth interview. We will also approach other key stakeholders including clinicians in leadership positions who may not have participated in the monitoring system. These interviews are intended to gather qualitative data on the facilitators and barriers to use and uptake of the monitoring system. Purposively sampling will be used to approach midwives with high use of the system and low use of the system. *See Appendix 3 – Clinician Interview guide.* Interviews will occur in a private room. Interviews will occur at a time convenient to clinicians (within one week of interaction or observation with the wireless monitoring system) so as not to interrupt clinical care. A digital recorder will be used to record interviews and the trained research assistant will then transcribe and translate interviews administered to clinician and post-partum women participants.

15. During the study period approximately 20 of the enrolled midwives will be observed using the wireless monitoring system to determine time performed to perform the steps for initiating monitoring for a woman. *See Appendix 5 – Time Tracking Form.*

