Aim 1: The primary outcome measure is the rate of severe maternal outcome (SMO). This is a composite measure drawn from WHO near miss morbidity criteria (Table 2). Secondary outcome measures include: the maternal mortality rate, maternal near miss rate and case fatality rates for postpartum hemorrhage, hypertensive disease and sepsis – the three most common causes of maternal death. The event rates for both primary and secondary outcomes will be compared using logistic regression models with the Generalized Estimating Equations approach to take into account of patients within clustering (due to time blocks). Exploratory analyses will be used to determine if a) the intervention is more powerful in certain subgroups of women and b) if any provider was consistently different in maternal outcomes regardless of intervention. The interaction between study arm and comorbidities (HIV, hypertension, pulmonary, cardiac or kidney disease, malaria) or provider will be tested in the logistic regression models. Subgroup effects will be reported if there is strong evidence of heterogeneity of intervention effect

Aim 2: We will apply the RE-AIM model to conduct a quantitative evaluation of the implementation of the intervention used in Aim. Table 4 describes the primary metrics to be measured and data sources from which it will be collected.

RE-AIM Implementation Science Framework ^{37,38}			
Metric	Dimension	Study Measure	Data source
Reach	Proportion of target population that participated in the intervention	
 Percent of women with successful placement of biosensor after delivery Total length of time for monitoring over 24hrs postpartum Percent of women participating in monitoring for 24 hrs 	
 Physiologic data from biosensor Time of delivery from chart records & theatre log books
Efficacy	Success rate if implemented as in guidelines	
 Percent of women with HR, BP, RR and Tp available at least every 4 hours for 24 hrs after delivery Percent of appropriate SMS alerts sent 	
 Physiologic data from biosensor RA review of mobile phones for SMS alerts and time of receipt

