## Study Objectives and Summary

Protocol title:	Wireless Physiologic Monitoring Among Postpartum Women
Design:	Single site, prospective pragmatic type 2 hybrid effectiveness-implementation trial utilizing a quasi-experimental, interrupted time series with repeated on/off periods
Study arms:	Repeated on/off intervention-control periods in 2-week blocks. Intervention group to receive wireless monitoring, and Control group to receive standard of care.
Population:	Women aged 18 and older undergoing emergency cesarean delivery at MRRH
Sample size:	Approximately 1266 women (633 per arm); dependent on clinical volume during blocks
Study sites:	Mbarara Regional Referral Hospital, Mbarara
Aim 1:	To estimate the clinical effectiveness of wireless physiologic monitoring of women in the first 24 hours after cesarean delivery at a referral hospital in a RLS.
Aim 2:	To evaluate the clinical adoption of wireless physiologic monitoring in a RLS using an implementation science approach using the RE-AIM Implementation framework.
Aim 3:	To use qualitative methods to explore clinical adoption by doctors and acceptability of wireless physiologic monitoring among postpartum women in RLS and understand facilitators and barriers to uptake of wireless physiologic monitoring.

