#### Protocol Deviations

Protocol deviations will be summarized in frequency tables

**Aim 1: To estimate the clinical effectiveness of wireless physiologic monitoring of women in the first 24 hours after cesarean delivery**

**Exposure** Intervention arm

**Primary outcome** Severe Maternal Outcome

**Endpoint** Discharge from hospital

**Descriptive statistics:** Proportion of women with one or more SMO, overall and by arm.

**Inferential statistics:** SMO will be statistically compared by arm using a Poisson model.

An intention to treat approach will be used to assess effectiveness. Thus, all women eligible for monitoring during an intervention arm including those who 1) declined consent 2) were missed from screening 3) were screened and not enrolled 4) enrolled but did not receive the intervention will be included in the intervention. The event rate for the primary and secondary outcomes will be calculated during the intervention and control time periods on all eligible women during those time periods. While intervention allocation was at the level of the two-week time period, the analysis will be at the individual patient level adjusting for clustering of observations within time periods. Using a logistic regression mixed effects model, with random effects to account for time block, we will compare the rate primary outcome between the intervention and control time periods.

Exploratory analyses will be used to determine if the intervention has a more significant effect in certain sub- groups of women (e.g. women <35, or women with more education). The interaction between study arm and comorbidities (i.e., HIV, hypertension, pulmonary, cardiac or kidney disease, malaria) will also be tested in logistic regression models. Subgroup effects will be reported if there is strong evidence of heterogeneity of intervention effect.

**Commented [BAA3]:** Intervention time periods will include women who  
-Declined consent  
-Were missed from screening  
-Were screened and unable to enroll  
-Enrolled but did not get the “full intervention”  
-Screened and enrolled – deceased before monitoring  
-Women ineligible due to language but those women will not be known in the control group.

**Commented [BAA4]:** Random effects for week using a mixed effects model  
Vs GEE where you put in clustering or correlation

**Commented [BAA5]:** Account for missing data in control period  
- impute for variables that are available and are independent for the intervention  

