- Use information from other people with the same arm  
- Create a missing category and use that as one the variable  
- Control for variables that are available in the chart

NCT ID: 2019P000885

Document Date: September 26th 2021

**Aim 2: To evaluate the clinical adoption of wireless physiologic monitoring in a RLS using an implementation science approach using the RE-AIM Implementation framework**

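### The primary comparison of alternating, non-randomised blocks should pre-specify a short baseline-adjusted model, because the risk factors are already being extracted from charts

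*SAP*

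**What the plan says.** *Allocation.* The SAP (Study Objectives and Summary) describes the design as "quasi-experimental, interrupted time series with repeated on/off periods". The allocation rule in the protocol (Study Procedures, item 4) begins "Alternative two-week blocks will be assigned to" and names the intervention and control conditions. No randomisation is described. The protocol's Sample Size section plans 13 blocks per arm.

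*Primary model.* Three statements exist:
- SAP, Aim 1, inferential statistics: "SMO will be statistically compared by arm using a Poisson model".
- The same section, a paragraph later: "Using a logistic regression mixed effects model, with random effects to account for time block", leading to "we will compare the rate primary outcome between the intervention and control time periods".
- Protocol, Biostatistical Analysis, Aim 1: "logistic regression models with the Generalized Estimating Equations approach", with time blocks as clusters.

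None names a baseline covariate or a calendar-time term. Comorbidities enter only through exploratory interaction tests.

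*Available data.* Protocol, Study Procedures, item 12: "The research assistant will also extract data on (age, district of origin, education level, occupation, referred in from another facility". The item goes on to parity, gestational age, antenatal complications, HIV, chronic hypertension and cardiac, pulmonary or kidney disease.

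*Where adjustment is mentioned.* A margin comment in SAP Aim 1 on missing control-period data lists several options, one of which is "Control for variables that are available in the chart". The plan text does not take it up. The SAP's Baseline Data section only describes the arms, and a margin comment there asks whether balance should be tested.

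**The concern.** With alternating blocks there is no randomisation to guarantee that case mix is balanced in expectation, and 26 blocks are few. If referred, hypertensive or high-parity women are unevenly spread, an arm-only model attributes the resulting difference in SMO to monitoring.

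Ascertainment may also differ by arm. In intervention blocks a research assistant approaches women in labour; controls are found by record review. A margin comment in SAP Aim 1 notes that women ineligible because of language will not be known in the control group.

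Finally, with no covariate list fixed, an imbalance seen in the baseline table would leave two poor choices: report an unadjusted quasi-experimental result, or pick covariates after seeing the data.

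**Working it through.** **1. The plan's own figure.** Inputs from the protocol's Sample Size section: 13 blocks of 95 per arm (13 × 95 = 1,235), ICC 0.01, baseline SMO 13%, two-sided 0.05, 80% power.
- Design effect 1 + 95 × 0.01 = 1.95; 1,235 / 1.95 = 633, as stated. The usual 1 + (95 − 1) × 0.01 = 1.94 gives 637.
- At 633 per arm, the two-proportion normal approximation gives a detectable increase of 5.75 points and a detectable reduction of 4.84 points. The stated 5.7 reproduces as an increase and is conservative for a reduction.

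**2. Chance imbalance in one risk factor.** Assume 30% prevalence and the same ICC as the outcome; the documents give no covariate ICC.
- SE of the arm difference = √(2 × 0.3 × 0.7 / 633) = 2.6 points.
- Mean absolute imbalance = 0.8 × 2.6 = 2.1 points; 95% edge = 1.96 × 2.6 ≈ 5 points.
- Covariate ICC 0 (n = 1,235): SE 1.8, edge 3.6 points. Covariate ICC 0.05 (design effect 1 + 94 × 0.05 = 5.7): SE 4.4, edge 8.6 points.

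**3. Shift in the SMO difference.** Assume SMO risk of 10% without the factor and 20% with it; 0.7 × 10% + 0.3 × 20% = 13%, matching the planned baseline. Shift = imbalance × 0.10.
- Typical: 2.1 × 0.10 ≈ 0.2 points, about 4% of 4.84.
- 95% edge: 5 × 0.10 = 0.5 points, about 10% of 4.84. With covariate ICC 0 or 0.05 the edge is about 0.4 or 0.9.
- Wider range, relative risk 2–3 and prevalence 20–30%, using 13% / (1 + prevalence × (RR − 1)) × (RR − 1) × imbalance: imbalances of 2, 5 and 10 points give shifts of 0.2–0.4, 0.5–0.9 and 1.0–1.9 points.

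**4. Share of the existing standard error.** For 13% vs 8.2% at 633 per arm, SE = √((0.13 × 0.87 + 0.082 × 0.918) / 633) = 1.73 points. The shift has SE 2.6 × 0.10 = 0.26 points. (0.26 / 1.73)² ≈ 2% of the variance; removing it narrows the SE by about 1%.

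**5. Time trend.** With strict alternation over 26 blocks, the arms' average positions differ by one block. A linear trend of T points over 25 steps leaves T / 25: 0.08 points for T = 2 and 0.24 for T = 6.

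**6. Power.** Simulation of 26 alternating blocks of 95 (1,500 runs per scenario; logistic model with cluster-robust SE; two risk factors with odds ratios 2 and 3 and prevalences 30% and 20%; true 13% vs 7.3%; three assumed splits of between-block variation).
- Power without and with adjustment: 0.939 to 0.945, 0.963 to 0.983, 0.972 to 0.982.
- With no true effect, the mean unadjusted log odds ratio stayed within 0.007 of zero.
- The SE of the log odds ratio barely moved (for example 0.165 vs 0.166) while the estimate went from −0.649 to −0.673, because the adjusted odds ratio is conditional.
- These scenarios start near the power ceiling. By approximate formula for 13% vs 18.7%, power of 0.80 becomes 0.82–0.84 if covariates explain 5–10% of outcome variance, and 0.85, 0.89 or 0.94 if they cut the residual ICC to 0.0075, 0.005 or 0.0025. All of these are assumptions.

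**7. Events available.** 1,235 × (0.13 + 0.073) ≈ 251. At the SAP's 633 per arm and 13% vs 8.2%: 633 × (0.13 + 0.082) ≈ 134.

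**The case against.** The strongest reply is that steps 2 and 3 measure chance, not bias. Random imbalance is already part of the unadjusted standard error, and one such factor adds only about 2% of its variance. Strict alternation interleaves the arms over a year, and the SAP counts all eligible women, including decliners and those missed at screening. Both limit systematic confounding, and steps 5 and 6 agree. This stands. A reader might infer that the unadjusted comparison is confounded, or that 0.5 points is an error on top of the confidence interval; the documents support neither.

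A second reply is that data may not be equally available. The SAP's margin comment expects missing control-period data. Protocol Study Procedures item 11 describes chart review for enrolled participants, and the consent waiver is requested for control record review, while the SAP's intention-to-treat set also includes intervention-period women who declined or were missed. This stands too: it shortens the covariate list and calls for a missing-data rule.

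Third, the margin comment is one of several undecided options. A reader might infer that the sponsor considered and rejected adjustment; the text shows only that the matter was left open.

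None of this supplies a reason for leaving collected risk factors out of the primary model of a non-randomised comparison.

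**Conclusion.** The point holds as a recommendation to improve the analysis, not as a finding that the planned result would be invalid. No stated primary model adjusts for baseline risk or calendar time, although blocks are not randomised and suitable variables are collected.

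Under the assumed 10% vs 20% risks, a 30%-prevalent factor typically shifts the SMO difference by about 0.2 points, and by 0.5 at the 95% edge. The simulated power gain is about 1 to 2 points, larger mainly if the covariates explain between-block variance. Covariate effects and covariate ICCs are assumptions, since the documents give none.

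Adjustment would reduce, not remove, the influence of measured case mix and of arm-dependent ascertainment. It does nothing for unmeasured factors or for women never identified in control blocks. The main benefit is that the covariate choice is settled before results are seen.

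**What to change.** In SAP Aim 1, replace the competing model statements with one primary model containing:
- arm and block clustering;
- a calendar-time term, which the interrupted time series label calls for;
- a short fixed list of pre-delivery chart variables recorded the same way in both arms, for example age, parity, gestational age, referral in, HIV, chronic hypertension and antenatal complication.

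Size the list to the expected events: about 250 at the protocol's numbers, but only about 134 at the SAP's 1,266 women.

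Report a marginal risk difference, so that adjusted and unadjusted results are on the same scale, and keep the unadjusted model as a sensitivity analysis. Specify multiple imputation for missing covariates, with missingness tabulated by arm, and resolve the margin comment accordingly. State how covariates will be obtained for eligible intervention-period women who declined or were missed.

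The cost is SAP wording and a little more analysis work. The downside is that covariate missingness may differ by arm, and imputation cannot fully repair that.

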**Descriptive statistics:**

Descriptive statistics will be analyzed according to the RE-AIM Framework as below.

**Reach:** Proportion of target population that participated in the intervention

- *Percent of women with successful placement of biosensor after delivery*
  - Determined by number of women with monitoring data from CH/ Number of women enrolled in Redcap
- *Time to initiation of monitoring*
  - Time from delivery date & time until start time of monitoring as recorded by RA in enrollment log
  - Time from delivery date & time until start time of vital sign data received by current health
  - Time from delivery date and time until start time of valid vital sign data from current health.
- *Total length of time of monitoring*
  - Length of time women wore the monitor, calculated from start/stop times recorded by RAs (mean  $\pm$  SD, median, IQR)
  - Length of time of vital sign data received by monitor, calculated from vital sign data received by CH (mean  $\pm$  SD, median, IQR)
  - Length of time of valid vital sign data received by monitor, calculated from vital sign data received by CH after excluding implausible values.
- *Percent of women participating in monitoring for 24 hours*
  - Number of women wearing the monitor for  $\geq 24$  hours / Number of women enrolled
  - Number of women with vital sign data received by monitor for  $\geq 24$  hour/Number of women enrolled.

**Efficacy:** Success rate if implemented as in guidelines

- *Percent of women with HR, BP, RR and Tp available at least every 4 hours for 24 hours after delivery*
  - *Intent to treat:*
    - Number of women with HR (RR, Tp) measured every 4 hours for 24 hours/ Number of eligible women in block
    - Number of women with BP measured every 6 hours for 24 hours/Number of eligible women in block
  - *Actual allocation*
    - Number of women with HR (RR, Tp) measured every 4 hours for 24 hours/ Number of women with CH output
    - Number of women with BP measured every 6 hours for 24 hours/ Number of women with CH monitoring

**Commented [BAA6]:** Restrict to women in block vs women eligible

NCT ID: 2019P000885

Document Date: September 26th 2021

- *Percent of appropriate alerts sent (restricted to those with CH output)*
  - Number of women with alerts sent for HR (RR, Tp, BP)/ number of women with CH monitoring
  - Number of women with “appropriate” alerts sent for HR (RR, Tp, BP)/ number of

Predefined limits for clinician alerts	
Physiologic sign	Cut off for alert
Heart rate (beats per minute),	Mean >120 beats per minute for 10 minutes
Systolic blood pressure (mmHg), any	>160 or <70
Diastolic blood pressure (mmHg), any	>110 or <30
Temperature (C)	Mean ≥ 38C for 10 minutes
Respiratory rate (breaths per min)	Mean ≥ 30 breaths per minute for 10 minutes

women with CH monitoring. (Appropriate defined as meeting the thresholds established by study protocol as in below)

- *Percent of alert receipt*
  - Number of alerts noted as received/Number of alerts sent. (Alerts received retrieved from midwife survey data on redcap using date/shift to collate; alerts sent from CH collated by date/shift.

**Adoption:** Proportion of practitioners adopting this intervention

- *Percent of eligible clinicians participating in wireless monitoring*
  - Midwives
    - Number of eligible midwives consenting/Number of eligible midwives
    - Number of midwives receiving phone/Number of eligible midwives scheduled
    - Number of midwives logging into system per shift/ Number of eligible midwives per shift (**Requires access to CH backend data on user logins and signing into on duty**)
- *Number of clinical actions in response to alerts – based on data from redcap surveys.*
  - Midwives
    - Time to review of alert
      - Proportion of alerts received reviewed <5 minutes, <15 mins, < 30 mins, 1 hr or ≥)
    - Proportion of patients assessed after report of an alarm (using end of shift survey data)
    - Proportion of patients with a clinical exam/procedure after report of receipt of an alarm (using end of shift survey data)
    - Proportion of patients with escalation in notification after report of receipt of an alarm (i.e., notification of someone else)

RE-AIM Implementation Science Framework			
Metric	Dimension	Study Measure	Data source
Implementation	Extent to which the intervention is	• Fidelity of implementation to the study protocol	• Documentation of any necessary adjustment to

NCT ID: 2019P000885

Document Date: September 26th 2021

	implemented in the real world		the protocol after study enrollment begins • Documentation of disruptions due to external factors
Maintenance	Sustainability of program over time	• Sustainability of reach, efficacy and adoption as measured by stability of measures over study period	• Above sources reviewed over the 12-month study period

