The wireless monitor to be used is a wearable wireless vital sign monitor called Current™. The device provides continuous real-time transmission of oxygen saturation, respiration rate, pulse rate, temperature, motion and activity, and posture captured every 2 seconds. It is integrated with the Omron Evolv blood™ pressure cuff to allow automated capture of blood pressure. Physiologic data from the sensor is transmitted via WiFi to a secure cloud storage (hosted by Amazon Web Services). Current™ is fully HIPAA¹ compliant and HITRUST² certified and has received US FDA approval. Physiologic data can then be accessed via a secure password protected mobile phone app or displayed on a monitor for real-time viewing. Pre-defined criteria can be used to program alerts or notifications should vital signs fall outside of the range. These notifications can be received via SMS or a mobile app notification. Notifications can be sent to multiple providers at a time. Providers can also log on or off from the device corresponding to their duty shifts.

To complete Aim 1, we will enroll all willing attending doctors and staff midwives with clinical duties covering the maternity ward, emergency cesarean delivery and postoperative care during the study period to use the wireless physiologic system and receive message alerts. Due to staffing the numbers of clinicians may fluctuate during the enrollment period. We will also enroll 1235 women undergoing emergency cesarean delivery during the study period during intervention blocks to wear a wireless physiologic monitor for 24 hours after birth. An additional 1235 women, also undergoing emergency cesarean during the study period during non-intervention blocks, will form a control group and have medical record review only. *We request to waive consent for this record review only.* Clinicians and peripartum women participating in wireless physiologic monitoring will form the same participants for Aim 2, which will involve participant observation, record review, and retrieval of data from the wireless monitoring system and clinician responder phones. To complete Aim 3, We will perform semi-structured interviews on 30 clinicians and 30 postpartum women drawn from

¹ HIPAA: Health Insurance Portability and Accountability Act of 1996) is United States legislation that provides data privacy and security provisions for safeguarding medical information

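### The SAP never computes the protocol's four-sign, 4-hourly Aim 2 efficacy percentage: under that heading it counts blood pressure every 6 hours, on a separate line from the other signs

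*SAP*

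**What the plan says.** The protocol (Biostatistical Analysis, Aim 2, RE-AIM table, Efficacy row) lists as a study measure: "Percent of women with HR, BP, RR and Tp available at least every 4 hours for 24 hrs after delivery". The SAP (Aim 2, Descriptive statistics, Efficacy) carries this over almost word for word as its heading: "Percent of women with HR, BP, RR and Tp available at least every 4 hours for 24 hours after delivery". Both place it in the efficacy dimension, which the SAP describes as "Success rate if implemented as in guidelines".

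Under the heading the SAP gives two sets of lines. In the intent-to-treat set, three signs are counted as "Number of women with HR (RR, Tp) measured every 4 hours for 24 hours/ Number of eligible women in block" and BP as "Number of women with BP measured every 6 hours for 24 hours/Number of eligible women in block". In the actual-allocation set, BP is again 6-hourly: "Number of women with BP measured every 6 hours for 24 hours/ Number of women with CH monitoring". Neither document gives a reason for the 6-hour BP interval.

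The analysis is descriptive ("Descriptive statistics will be analyzed according to the RE-AIM Framework as below"). No test, target or sample size attaches to this measure. On how BP is obtained, the protocol (Study Intervention) says only that the wearable is "integrated with the Omron Evolv blood™ pressure cuff to allow automated capture of blood pressure". It gives no cuff cycle.

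**The concern.** A heading and the counts beneath it should describe the same quantity. Here they differ in two ways.

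- **Interval.** The heading applies one 4-hour interval to four signs. The BP lines use 6 hours. Because this occurs under both denominators, a single typing slip is unlikely.
- **Combination.** The heading reads most naturally as one percentage of women with four signs. The lines beneath it give BP apart from the other three, and the notation for those three looks like one count per sign. No line requires the same woman to meet all four.

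An analyst who follows the SAP therefore cannot report the measure that the protocol pre-specified. This is so even on a sign-by-sign reading, because 4-hour BP is not counted anywhere. If the available figures were placed under the heading, a reader would take them as meeting a stricter standard than was applied. The mismatch would carry into two further uses: the comparison of RE-AIM measures by provider (protocol, Aim 2), and the maintenance dimension, which both documents define through stability of reach, efficacy and adoption over the study.

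**Working it through.** The documents give no expected value for this measure, so there is no figure to reproduce. The check has three parts: set the definitions side by side, establish the direction of any error, and illustrate its size under stated assumptions.

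**1. Definitions**

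| Place | Signs | Interval | All four in the same woman? |
|---|---|---|---|
| Protocol, RE-AIM table | HR, BP, RR, Tp | at least every 4 h | natural reading, not stated |
| SAP heading | HR, BP, RR, Tp | at least every 4 h | natural reading, not stated |
| SAP lines, first sign group | HR (RR, Tp) | every 4 h | BP not included |
| SAP lines, BP | BP | every 6 h | BP only |

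The BP-alone 4-hour count and the four-sign count are both absent.

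**2. Direction**

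- 24/4 = 6 windows and 24/6 = 4 windows, so the 6-hour criterion is the looser one.
- A woman with no BP gap above 4 h has no gap above 6 h. Hence P(BP at 6 h) ≥ P(BP at 4 h).
- A woman who meets all four signs meets each one. Hence P(any single sign) ≥ P(all four).
- Example: BP at 0, 5, 10, 15 and 20 h has a longest gap of 5 h. It fails the 4-hour criterion and passes the 6-hour one.

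Measured against the heading, any error is upward or zero.

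**3. Size of the BP interval effect (assumptions, not trial data)**

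Suppose BP is attempted at a fixed spacing, each attempt succeeds independently, and a woman qualifies if her longest gap from delivery to 24 h is within the limit. Simulation of 200,000 women per setting gives:

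| Attempts | Success | Meets 4 h | Meets 6 h | Excess (points) |
|---|---|---|---|---|
| hourly | 70% | 88.8% | 99.0% | 10.2 |
| 2-hourly | 70% | 45.9% | 82.7% | 36.8 |
| 2-hourly | 90% | 91.2% | 99.2% | 8.0 |
| 4-hourly | 90% | 59.2% | 59.2% | 0 |
| 6-hourly | 90% | 0% | 72.8% | 72.8 |

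Two rows can be checked by hand. With 4-hourly attempts, one miss makes an 8-hour gap that fails both limits, so both proportions are 0.9^5 = 0.590 (five attempts, at 4 to 20 h). With 6-hourly attempts, the 4-hour limit can never be met, and the 6-hour limit needs three successes (6, 12 and 18 h): 0.9^3 = 0.729. Both agree with the simulation. An exact calculation of every row agrees to within 0.2 points.

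**4. Size of the separate-versus-joint effect (assumption: each sign alone reaches proportion p)**

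The joint proportion lies between max(0, 4p − 3) and p, and equals p^4 under independence.

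- p = 0.9: 4 × 0.9 − 3 = 0.60, so 60% to 90%; 0.9^4 = 65.6%.
- p = 0.8: 4 × 0.8 − 3 = 0.20, so 20% to 80%; 0.8^4 = 41.0%.

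The upper end, where nothing is lost, occurs when the same women fail on every sign.

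**The case against.** The strongest defence is that each SAP line names its own sign and interval. Reported as written, each figure is true for what it says, and nothing in the documents states that the lines will be merged or presented as one 4-hour four-sign result. That stands. A reader might infer that Aim 2 efficacy will be overstated; the documents support only that it may be, if these figures are reported under the heading.

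Further points for the defence:

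- **The joint reading is not explicit.** Neither document says that all four signs must be met by the same woman. The SAP uses similar shorthand in its alert lines, so sign-by-sign reporting may be its convention. This stands, and is why the SAP should say which it means. It does not rescue the BP line, which departs from 4 hours on either reading.
- **BP need not be the weakest sign.** It is tempting to infer that the cuff fails most often and that the standard was relaxed where it would hurt. The protocol says that respiration, pulse and temperature are captured every 2 seconds and that BP comes from an integrated automated cuff. It gives no failure rate, so the inference is unsupported.
- **This is not shown to be the main measure.** The protocol lists it beside the alert measure without ranking, and the reach measures also describe delivery of monitoring.
- **The illustrative sizes are soft.** Independence is doubtful for signs that share one wearable, and every range includes zero or near-zero excess. This stands; the figures show what is possible, not what is expected.

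**Conclusion.** The point holds in a limited form. The SAP contradicts its own heading and the protocol on the BP interval, 6 hours against 4, under both denominators, and contains no line that yields the protocol-defined percentage. That rests on the text alone.

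Whether a published figure would be too high depends on how the lines are labelled. If they appear under the heading, the error is upward or zero. Its size turns on cuff scheduling, BP completeness and the overlap of failures between signs, none of which the documents give. In the assumed scenarios tabulated, the BP excess runs from 0 to about 37 points when attempts are 4-hourly or more frequent, and reaches about 73 points with a 6-hourly cuff cycle and 90% success. The separate-versus-joint difference runs from 0 to 30 points if each sign alone reaches 90%.

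The scope is one descriptive efficacy measure of Aim 2, together with the provider and maintenance summaries that use it. The alert measures are separate. The Aim 1 comparison and its power are untouched. Which BP interval is appropriate is not judged here.

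**What to change.** 1. Reconcile the BP interval between the protocol and the SAP, and record the reason and date for any change.
2. State whether the efficacy measure is joint (all four signs in the same woman), per sign, or both.
3. Add two counts for each denominator the SAP uses: women with all four signs at least every 4 hours for 24 hours, and women with BP alone at that interval. The two actual-allocation lines word their denominator differently (device output, device monitoring), and a margin comment leaves open the choice between women in the block and eligible women. Settle both at the same time.
4. Keep the single-sign rates and the 6-hour BP rate, each under a label giving its own sign and interval.

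The cost is a few lines of SAP text and analysis on data already collected. The downside is a possibly less favourable headline percentage.
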